### 8.7. Safety analyses

Adverse events (AEs) will be presented in per-patient data listings and summarized in frequency tables. A summary table will be presented with number of patients with:

- AEs
- serious AEs
- related AEs
- AE leading to discontinuation

for each treatment and in total.

Adverse events (AEs) will be presented in per-patient data listings and summarized in frequency tables by treatment and in total. AEs will be summarized as number of events and number of patients, respectively, by intensity, seriousness and relationship. SAE will be presented in a separate listing.

Safety profile will be evaluated by comparing number (%) of adverse event (AE) and serious adverse events (SEA) in each group. Difference between groups in safety profile will be compared with Chi2-test or when appropriate, Fischer's exact test.

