16.2 RISK - BENEFITS

A risk analysis for this study has been made. These risks together with the actions to minimize these risks are compiled below:

	Anticipated risk	Action
1	Side effects such as minor behavior problems (mood changes), sleep disturbances, nausea or vomiting	Reported as Adverse Events and follow up until recovered. A Development Safety Update Report (DSUR) will be presented yearly to MPA
2	Trauma for the child to take medicine	Capsules may be opened and the content can be mixed with something tasty. The study nurse will instruct the parents/guardians when study medication is distributed and will also follow up how it works by telephone calls one and two weeks after Baseline
3	No effect on the recovery rate	There is no alternative treatment, why there is no risk that the patient looses an effective treatment by participating in the study

A short-course oral treatment with corticosteroids (defined as 1-2 mg/kg once daily in 7-14 days) is not associated with major side effects, such as risk of growth retardation, osteoporosis or diabetes mellitus in children, but may be associated with minor side effects, such as behavioral problems (mood changes), sleeping disturbances, nauseas or vomiting in 4,3 – 5,4 % of cases (17,25,26).

The risk of minor side effects will be reduced with the dose $1 \text{ mg/kg} \times 1$ (17), as we plan on using in the present study.

Increased susceptibility to infection (<1%) is the most frequent (S)AEs associated with short courses of corticosteroids (25,26). In five large RCTs on short-course corticosteroid treatment, three children with varicella infection needed intensive care due to complications (25).

Parents/guardians will be informed before start of treatment in the current study about the importance to attend health care if fever or signs of infection occur during the study period.

In summary, the benefits, i.e. possibly improved recovery of the facial nerve palsy are anticipated being higher than the risks.

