###### 5.1.2. Secondary Objective(s)

The secondary objectives are:

- to evaluate the total recovery rate at 1 month as compared to the total recovery rate at 12 months, in order to evaluate if prediction of recovery at 1 month is feasible and/or useful in children with acute facial nerve palsy
- to evaluate subjective symptoms and influence in daily life in children with acute facial nerve palsy
- to evaluate the safety profile for cortisone in children with acute facial nerve palsy

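### SAP 8.7 judges safety on pooled AE and SAE counts and pre-specifies no grouping or by-arm comparison by kind of event, although protocol 16.2 names the harms expected

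*SAP*

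**What the plan says.** Safety is a secondary objective in both documents; SAP 5.1.2 words it as "to evaluate the safety profile for cortisone in children with acute facial nerve palsy".

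SAP 8.7 then sets out the outputs:
- Patient counts by arm for any AE, serious AEs, related AEs and AEs leading to discontinuation.
- Listings and tables: "Adverse events (AEs) will be presented in per-patient data listings and summarized in frequency tables by treatment and in total". The rows of these frequency tables are not stated.
- A breakdown: "AEs will be summarized as number of events and number of patients, respectively, by intensity, seriousness and relationship".
- The basis for comparing the arms: "Safety profile will be evaluated by comparing number (%) of adverse event (AE) and serious adverse events (SEA) in each group", by chi-squared or Fisher's exact test.

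Neither document mentions a coding dictionary, preferred terms, event groups or a classification step. Protocol 12.2 requires dates, intensity, action taken, relationship, outcome and SAE status for each AE, but no category. SAP 2 and SAP 13 refer output layouts to Appendix 1.

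Protocol 16.2 is specific about what to expect. Its risk table lists "Side effects such as minor behavior problems (mood changes), sleep disturbances, nausea or vomiting". The text below the table puts the minor effects, ending in "nauseas or vomiting in 4,3 – 5,4 % of cases", at a stated frequency for short courses of 1-2 mg/kg. It adds that "Increased susceptibility to infection (<1%) is the most frequent (S)AEs associated with short courses of corticosteroids".

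**The concern.** The plan names the harms it expects but does not connect them to an analysis. The stated between-arm comparison counts a child with vomiting, a child with a fracture and a child with a cold alike. Treatment lasts 10 days, but AEs are collected for 12 months (protocol 12) and include any untoward occurrence, accidents among them (protocol 12.1). Ordinary childhood illness therefore enters the count that is tested. A finding of no difference in AEs would then say little about sleep, mood or stomach effects, which families and guideline writers will ask about.

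If events are first sorted into kinds once the arms are known, the choice of groups can be shaped by the result. The related-AE count does not remove the problem, because it still merges vomiting with infection.

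**Working it through.** **Reading the text.** The dimensions named in SAP 8.7 are intensity, seriousness, relationship and discontinuation. Those in protocol 16.2 are behaviour or mood, sleep, nausea or vomiting, and infection. The two lists do not overlap, and no step in either document maps one to the other.

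**Inputs.** From the documents: 250 per arm (SAP 9), two-sided 5% (SAP 8), 4.3-5.4% for the minor effects and below 1% for infection (protocol 16.2). Assumed, because the documents give no such rates: placebo 1-3% for the minor effects combined, and a background of 30-70% of children with any AE.

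The documents give no safety power to reproduce. Their one power figure, 430 patients for 80% v 90% recovery, is consistent with Fisher's exact test (80.3% power at 215 per arm) and does not bear on this point.

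**Formula.** With d the difference, SE0 = √[2p̄(1−p̄)/n] and SE1 = √[p1(1−p1)/n + p2(1−p2)/n]:

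power = Φ[(d − 1.96·SE0)/SE1] + Φ[(−d − 1.96·SE0)/SE1].

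For any AE, an excess e falling independently on a background b gives a prednisolone rate of b + e(1−b).

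**Minor effects as one group, 1% v 5.4%.** p̄ = 0.032, SE0 = 0.0157, SE1 = 0.0156. (0.044 − 0.0309)/0.0156 = 0.84, so power is 80%.

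**The same 4.4-point excess inside any AE, background 50%.** Prednisolone rate 0.50 + 0.044 × 0.50 = 0.522; SE0 = SE1 = 0.0447. (0.022 − 0.0876)/0.0447 = −1.47 gives 7.1%; the other tail adds 0.7%, so power is 8%.

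| Placebo | Prednisolone | Excess (points) | Combined minor effects | Any AE, b = 30% | b = 50% | b = 70% |
|---|---|---|---|---|---|---|
| 1% | 4.3% | 3.3 | 63% | 9% | 7% | 6% |
| 1% | 5.4% | 4.4 | 80% | 11% | 8% | 6% |
| 2% | 4.3% | 2.3 | 31% | 7% | 6% | 5% |
| 2% | 5.4% | 3.4 | 52% | 9% | 7% | 6% |
| 3% | 4.3% | 1.3 | 12% | 6% | 5% | 5% |
| 3% | 5.4% | 2.4 | 27% | 7% | 6% | 5% |

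Fisher's exact test is more conservative with so few events. The combined group then has 55-77% power at 1% placebo, 23-44% at 2% and 8-20% at 3%.

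**A larger excess.** If 4.0-5.4 points are added to the any-AE background, pooled power runs from 6% (4.0 points, b = 70%) to 15% (5.4 points, b = 30%).

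**Single rows.** If the range covers the three minor effects together and splits equally (an assumption), each gains 1.4-1.8 points. Over 0.5-1% placebo, power is about 23-40%. Infection at 0.5% v 1% has about 10%.

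**What an interval would show.** For 1% v 5.4%, the difference is 4.4 ± 1.96 × 1.56 = 4.4 ± 3.1 points. For infection at 0.5% v 1%, SE1 = 0.0077, so it is 0.5 ± 1.5 points.

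**The case against.** A reader might infer that the trial cannot report these harms, or that kind of event survives only in patient listings. The documents support neither. Protocol 12.2 puts every new complaint on the AE form, and protocol 13.2 lists all CRF data by subject, so counts by kind and arm can be produced. The frequency tables in SAP 8.7 have unstated rows, and SAP 8 defines frequency tables as the summary for qualitative variables, which an AE term is. Appendix 1 may hold a by-type table. All of this stands, and it makes the point conditional.

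It does not remove the point. SAP 8.7 cites no particular output, whereas SAP 8.9 cites a numbered table in Appendix 1. A table shell alone also would not supply a blinded rule for sorting free-text complaints into groups.

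The second objection concerns size. Treating 4.3-5.4% as an excess over a 0.5-1% placebo rate gives 79-93% power, and a reader might take that as the power for each harm. Protocol 16.2 gives the range as a frequency of cases on steroids, attaches it to a list of effects, and expects lower risk at 1 mg/kg. The figures above therefore use it as the prednisolone-arm rate for the group, and single rows do much worse.

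Third, any AE is the least favourable comparator. SAP 8.7 also tabulates related AEs, which are the named safety endpoint. With an assumed related-AE background of 3-5% and 4.3-5.4 points added, that count would have about 43-72% power if compared. This narrows the sensitivity gap but leaves the kinds of harm merged.

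**Conclusion.** The point holds in a limited form. The SAP text pre-specifies no grouping of AEs and no summary or comparison by kind of event, and the between-arm comparison it does state is insensitive to the harms the protocol expects. Pooled power is roughly 6-15% for an effect added in about 4-5% of children. The combined minor effects have 63-80% at 1% placebo, 31-52% at 2%, and 12-27% at 3%.

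These figures rest on assumed placebo and background rates. At 3% placebo against 4.3% the advantage is small (12% v 5-6%), and the gain is then mainly an honest estimate with its interval. The conclusion is also conditional on Appendix 1, which was not available. No population, sample size or efficacy analysis is wrong. The change is worth making because it is cheap and uses data already recorded, not because reporting is otherwise impossible.

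**What to change.** In SAP 8.7:
1. State how AE terms will be grouped, and complete the grouping while blinded to arm.
2. Add a table of the number (%) of children with each kind of AE, by arm.
3. Pre-list the protocol 16.2 harms as rows (behaviour or mood, sleep, nausea or vomiting, infection), plus one combined row for the three minor effects.
4. Give each pre-listed row a risk difference with 95% CI, labelled exploratory, and say that single rows, infection in particular, are descriptive.

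If Appendix 1 already contains such a table, cite it by number in SAP 8.7 and add the blinded grouping step.

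The cost is one blinded grouping exercise, one output table and a few more exploratory intervals. Nothing changes for patients, sample size or the primary analysis.

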12 ASSESSMENT OF SAFETY

Safety will be evaluated by recording of routine laboratory tests (white and red blood cells, CRP, electrolytes and glucose), physical examinations, blood pressure and vital signs measurements. Adverse Events (AEs) or Serious Adverse Events (SAEs), will be reported if occurring during the study period (12 months).

Any clinically relevant changes and actions taken, for instance occurrence of an adverse event or administration of concomitant medication, will be recorded in the CRF and hence in the database.

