12.2 METHODS FOR ELICITING, RECORDING AND FOLLOW-UP OF ADVERSE EVENTS

Information regarding AEs is to be obtained by questioning or examining the subject after having signed the ICF. At each visit all new complaints and symptoms (i.e., those not existing prior to signing of informed consent) must be recorded on the AE CRF.

Pre-existing complaints or symptoms that increase in intensity or frequency after having signed the ICF must also be reported as an AE.

All AEs must be characterized in terms of their start and stop dates, maximum intensity, action taken on the study medication, relationship to study medication, subject outcome and whether or not the AE led to a SAE. Any clinically relevant increase or decrease to the intensity or frequency of a reported AE requires a separate entry on the AE form.

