#### 5.2.3. Secondary Endpoint(s)

Secondary endpoints are:

- the total recovery rate at 12 months follow-up in the two treatment groups measured with the Sunnybrook scale.
- The Sunnybrook scale (100 is normal function and 0 is total loss of function) is another objective scale for grading the facial nerve function. It will be used as secondary outcome measure. It is validated for children, easy to perform and has been used in previous studies. It correlates well to the House-Brackmann scale and has been shown to be useful for prediction of recovery in adult patients.
- the agreement between the two grading scales for facial impairment (House-Brackmann and Sunnybrook), in order to decide which grading scale has the most preferable utility and should be recommended in pediatric patients
- the total recovery rate at 1 month follow-up as compared to the total recovery rate at 12 months follow-up, measured with Sunnybrook and House-Brackmann scale (prediction).
- quality of daily life at 1 and 12 months follow-up measured with the Facial Clinimetric Evaluation (FaCE) scale and the Facial Disability Index (FDI) and at the 12 months measured with the Synkinesis Assessment Questionnaire (SAQ) and to correlate them to the physician assessed House-Brackmann and Sunnybrook grading scales .
- number of Adverse Events possibly or probably related to the study drug during the 12 months follow-up.

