### 8.3. Treatment Administration/Compliance

The intervention is treatment with either prednisolone (capsule Prednisolone 5 mg), 1 mg/kg once daily in 10 days or control treatment (capsule placebo) once daily in 10 days. The number of capsules is based on the child's weight and presented in the table below:

Child's weight /kg	Number of capsules/day	Total number of capsules
5 - 9.9	2	20
10 - 14.9	3	30
15 - 19.9	4	40
20 - 24.9	5	50
25 - 29.9	6	60
30 - 34.9	7	70
35 - 39.9	8	80
40 - 44.9	9	90
>45	10	100

Capsule Prednisolon 5 mg (APL), dosage 1 mg/kg (max 50 mg) once daily for 10 days according to pre-calculated weight. All bottles include 100 capsules.

Compliance for the 10 day period:

Compliance (0-100%) = (Number of tablets actually taken x 100)/total number of capsules

Patients with treatment compliance less than 70% will be excluded from the PP analysis. Patients with 0% compliance will be excluded from ITT analysis.

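### The safety endpoint is drug-related adverse events, but the between-group test in SAP 8.7 names only AEs and SAEs, and no treatment-period comparison is planned for a 10-day course

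*SAP*

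**What the plan says.** The endpoint lists in protocol 7.2 and SAP 5.2.3 give one safety endpoint, in the same words: "number of Adverse Events possibly or probably related to the study drug during the 12 months follow-up".

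SAP 8.7 handles related events descriptively. They have a line in a by-treatment table of patient counts, and "AEs will be summarized as number of events and number of patients, respectively, by intensity, seriousness and relationship". The inferential part is two sentences. The first sets the comparison: "Safety profile will be evaluated by comparing number (%) of adverse event (AE) and serious adverse events (SEA) in each group". The second gives the method: "Difference between groups in safety profile will be compared with Chi2-test or when appropriate, Fischer's exact test". Neither mentions relatedness.

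Treatment lasts 10 days (SAP 8.3), while protocol section 12 has AEs reported over the 12-month study period. SAP 8.7 sets no onset window, although protocol 12.2 requires that "All AEs must be characterized in terms of their start and stop dates".

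The only expected side-effect rate is in protocol 16.2, for short courses at 1–2 mg/kg: minor effects including "sleeping disturbances, nauseas or vomiting in 4,3 – 5,4 % of cases". The same section expects a lower risk at the study dose.

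**The concern.** Read literally, the plan tests something other than its stated endpoint. The tested quantity is broad: protocol 12.1 counts accidents, unplanned operations, medication changes and worsening of concurrent illness as AEs, and these accrue for a year after a 10-day course. A modest steroid effect is then diluted by background illness, and a non-significant p-value could be mistaken for reassurance. This matters because safety is part of the study aim in protocol 5.1, and a favourable trial result is meant to feed into guidelines.

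The unit of analysis is also loose. The endpoint is a number of events, and the comparison sentence speaks of a number and percentage of events. A chi-square or Fisher test needs independent units. Protocol 12.2 asks for a new entry whenever an AE changes relevantly in intensity or frequency, so one child's fluctuating symptom can yield several entries.

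**Working it through.** **The plan's own figure.** The documents give no power for safety; the sample size rests on recovery alone (SAP 9: 80% versus 90%, two-sided 5%, 80% power, 430 patients raised to 500). The 430 is sound. The two-proportion formula gives 199 per arm (398) without and 219 per arm (438) with continuity correction, and Fisher's exact test has 80.3% power at 215 per arm. For 10% loss, 430/0.90 = 478, which 500 covers.

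**Inputs from the documents.** n = 250 per arm (SAP 9); two-sided 5% (SAP 8); side-effect rate 4.3–5.4% (protocol 16.2).

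**Assumptions, because the documents give no placebo AE rates.** Placebo proportion of children with any AE over 12 months: 10–70%. Placebo proportion with a related AE: 1%, 2% or 5%. The 4.3–5.4% is first taken as the excess over placebo, e.

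**Formula.** With placebo rate p0, prednisolone rate p1, d = p1 − p0 and p̄ = (p0 + p1)/2:
- se0 = √(2p̄(1 − p̄)/n)
- se1 = √((p0(1 − p0) + p1(1 − p1))/n)
- power = Φ((d − 1.96·se0)/se1) + Φ((−d − 1.96·se0)/se1)

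Two models for p1: additive, p1 = p0 + e (side effects fall only on children with no other AE); independent, p1 = 1 − (1 − p0)(1 − e).

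**Any AE, most favourable case** (p0 = 10%, e = 5.4%, additive). p1 = 0.154, p̄ = 0.127, se0 = 0.0298, se1 = 0.0297. (0.054 − 1.96 × 0.0298)/0.0297 ≈ −0.15, so power is 44%.

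| Placebo any-AE rate (assumed) | Independent | Additive |
|---|---|---|
| 10% | 27–38% | 31–44% |
| 30% | 11–15% | 18–25% |
| 50% | 8–9% | 16–23% |
| 70% | 6–7% | 19–27% |

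**Related AE, example** (p0 = 2%, e = 4.3%, additive). p1 = 0.063, p̄ = 0.0415, se0 = 0.0178, se1 = 0.0177. (0.043 − 1.96 × 0.0178)/0.0177 ≈ 0.45, so power is about 68%.

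| Placebo related-AE rate (assumed) | 4.3–5.4% as excess | Same, Fisher's exact | 4.3–5.4% as total prednisolone rate |
|---|---|---|---|
| 1% | 79–90% | 75–89% | 63–80% |
| 2% | 68–82% | 62–79% | 31–52% |
| 5% | 46–62% | 41–57% | no meaningful excess |

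**Sensitivity.** With 10% loss (225 per arm), any-AE power is at most about 40%. Related-AE power (as excess) becomes 74–86%, 63–77% and 42–58% at 1%, 2% and 5%. For a 10-point excess at 250 per arm, the any-AE test has 61–88% power (additive) or 11–82% (independent).

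**The case against.** The endpoint is not ignored. Related AEs are counted per patient and by arm in SAP 8.7. Safety profile is also the term used in the safety objective, so the test sentence could be read to cover them. The output shells in Appendix 1 are not among the documents and might settle it. This stands as far as it goes: the gap is a missing named test. But SAP 8.5 and 8.6 tie the efficacy endpoints to explicit methods, and the safety endpoint deserves the same.

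No power is promised for safety, and protocol 13.2 allows tests for hypothesis generation. Low power for a secondary comparison is not in itself an error. That is also right, and the power figures serve only to show why the choice of tested quantity matters.

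The 4.3–5.4% is a rate of cases, not an excess over placebo, and the protocol expects less at the study dose. This stands, and it is why the total-rate column is shown. Relatedness is also a coarse filter: protocol 12.4 classes an AE as possibly related when the association is unknown and no other condition clearly explains it. The advantage of testing related AEs therefore shrinks as placebo reports rise.

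On the unit, the summary table does count patients, and a percentage beside a chi-square test usually means patients. A per-child test is probably intended; it is simply not stated.

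Two stronger inferences are tempting. A reader might conclude that the all-cause test cannot detect any steroid effect; the 10-point results show that a large excess could be found under some backgrounds. A reader might also treat the 12-month window as a slip in SAP 8.7. It belongs to the endpoint definition, so testing related AEs would not shorten it, and a treatment-period analysis has to be added separately.

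**Conclusion.** The point holds as a mismatch between endpoint and test. As written, related AEs are described by arm but no test is named for them, and nothing isolates the period around the 10-day course even though AE dates are recorded.

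The all-cause comparison has low power for a small effect: about 6–38% or 16–44%, depending on whether the excess is independent of background or adds fully. Related AEs do better, at 46–90% across placebo rates of 5% down to 1%, but only 31–52% at a 2% placebo rate if the protocol's figure is the total rate under prednisolone. All of this rests on assumed placebo rates and on reading 4.3–5.4% as an excess or a total. The direction of the contrast is firmer than any single figure.

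The documents do not support a claim that a null result would be presented as proof of safety, since related AEs by arm would be reported alongside it. Nor do they require the 12-month AE and SAE comparison to become purely descriptive: it does not depend on causality judgement and is worth keeping.

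**What to change.** In SAP 8.7:

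1. Name the comparison for the stated endpoint: the proportion of children with at least one possibly or probably related AE over 12 months, as a risk difference with 95% CI and a chi-square or Fisher's exact test.
2. Add the proportion of children with at least one AE of any cause with onset from first dose to the 1-month visit, analysed the same way. This does not rely on causality judgement. No power can be given for it, because the documents contain no first-month AE rate.
3. State that the child is the unit in every such test, with event counts reported descriptively.
4. Keep the planned 12-month AE and SAE comparison, and say that a non-significant result will not be read as evidence of no difference.

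The cost is SAP wording and one or two tables from relatedness and dates already collected. The downside is one or two more secondary comparisons.

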5.1 STUDY RATIONALE

Since no RCT has previously been performed on cortisone treatment in children with acute facial nerve palsy, there is a lack of evidence-based guidelines.

The aim of the FACE study is to evaluate the efficacy and safety of cortisone treatment given to children with acute facial nerve palsy in a randomized placebo-controlled trial.

If the cortisone treatment is shown to be beneficial for recovery in children with facial nerve palsy, cortisone treatment will be introduced in clinical practice and international evidence-based guidelines will be published.

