## **8. Description of statistical analysis**

All variables will be presented in summary tables and/or per-patients data listings (when appropriate) within treatment group and in total. Graphical presentations may be used if necessary. Descriptive statistics are defined as frequency (%) tables for qualitative variables and as number of observations, means, standard deviations, medians, Q1, Q3, and minimum and maximum values for quantitative variables. Normality of data will be determined by visual inspection of histograms. No adjustment for covariates will be made.

All statistical tests and confidence intervals will be two-sided. The level of significance will be 5%.

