### 8.5. Primary efficacy analyses

Efficacy of cortisone treatment versus placebo will be compared between intervention group and control group at 12-months follow-up, with the outcome measured with House-Brackmann. Recovery will be defined as HB=1. Comparisons between dichotomous variables (i.e. recovered/not recovered) will be performed between groups using Chi2 (or Fisher's exact test) with risk estimate and 95% confidence interval. Mann-Whitney U-test will be used when comparing score medians for the House-Brackmann grading scale.

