## 9. Determination of sample size

Sample size for the FACE study is calculated on the primary outcome (i.e. number (%)) of patients with total recover of the facial nerve palsy in each intervention group, measured by House-Brackmann grade 1, at 12 months follow-up). An 10% difference of the total recovery rate between groups (80% in placebo group versus 90% in prednisolone group) is an estimation from earlier non-RCT studies, interviews with children/parents (unpublished data) and a test of two independent proportions for estimation of the minimal relevant clinical improvement (MRC). To show that such a difference is significant ( $p < 0.05$ , two-sided test) with 80 % power, a total of 430 patients are needed. However, due to the uncertainty in the assumptions and to that a portion (10%) of patients not taking part of the study follow-up, 500 patients will be included in the FACE study (250 in each group).

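### SAP 8.7 names only a Chi2 or Fisher test for comparing safety between arms, without the effect estimate and confidence interval that 8.5 and 8.6 give for recovery

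*SAP*

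**What the plan says.** Safety is part of the trial's aim. Protocol 5.1 sets out to "evaluate the efficacy and safety of cortisone treatment given to children with acute facial nerve palsy", and the safety profile is a secondary objective in both documents. The declared safety endpoint (Protocol 7.2, SAP 5.2.3) is the number of AEs possibly or probably related to study drug over 12 months.

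SAP 8.7 plans per-patient listings, frequency tables by intensity, seriousness and relationship, a separate SAE listing, and a summary of patients with AEs, serious AEs, related AEs and AEs leading to discontinuation, by arm. It then says: "Safety profile will be evaluated by comparing number (%) of adverse event (AE) and serious adverse events (SEA) in each group". The inferential step follows: "Difference between groups in safety profile will be compared with Chi2-test or when appropriate, Fischer's exact test". The section mentions no risk difference, risk ratio or interval.

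For recovery, SAP 8.5 has the comparison "performed between groups using Chi2 (or Fisher's exact test) with risk estimate and 95% confidence interval", and 8.6 does the same for the Sunnybrook scale. SAP 8 makes all tests two-sided at 5%.

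SAP 9 derives the sample size from recovery only (80% v 90%, 430 patients, raised to 500, 250 per arm). Neither document states a power or a precision for any safety comparison. The nearest figure to a serious-event rate is in Protocol 16.2: "Increased susceptibility to infection (<1%) is the most frequent (S)AEs associated with short courses of corticosteroids". That is one type of event, not a total SAE rate and not a placebo rate.

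**The concern.** A test of no difference is informative about harm only if the trial would be likely to detect a harm that matters. This trial was sized for a 10-point difference in a common outcome, and serious events are likely to be few. A non-significant result is then the likely outcome whether or not prednisolone raises the SAE rate, and the p-value cannot separate the two cases. An interval can, because it shows how large an excess remains compatible with the data.

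The safety result will be used. Protocol 5.1 says that if cortisone proves beneficial it will enter clinical practice and international guidelines will follow. As planned, the only pre-specified inference on safety that would accompany an efficacy finding is a p-value.

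**Working it through.** **Inputs**
- Arm size 250, 1:1 (SAP 9); two-sided 5% (SAP 8); 10% loss to follow-up (SAP 9).
- Placebo SAE rate: not given. Assumed at 0.5%, 1%, 2% and 3%. The SAE definition in Protocol 12.5 includes inpatient hospitalisation whatever the cause (elective and pre-planned admissions apart), and events are reported over 12 months (Protocol 12), so a rate above 1% is possible.
- Scenario: prednisolone doubles the placebo rate.

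**1. The plan's own figure.** For 80% v 90%, with mean proportion 0.85:

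n per arm = [1.96·√(2·0.85·0.15) + 0.842·√(0.8·0.2 + 0.9·0.1)]² / 0.10² = 199, or 398 in total.

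With a continuity correction it is 219 per arm, or 438 in total. The SAP's 430 lies between these, 1.9% below the corrected figure (8/430). Allowing for 10% loss, 430/0.90 = 478, which 500 covers. The efficacy size is sound; nothing in it concerns safety.

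**2. Chance that a true doubling is non-significant.** Let X (placebo) and Y (prednisolone) be independent binomial counts with n = 250 and rates p and 2p. The miss rate is 1 minus the sum of P(X=x)·P(Y=y) over all pairs (x, y) whose test gives p<0.05. Exact enumeration, with Chi2 uncorrected:

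| Assumed placebo rate → prednisolone | Missed, Fisher | Missed, Chi2 |
|---|---|---|
| 0.5% → 1% | 98.7% | 92.3% |
| 1% → 2% | 93.2% | 86.5% |
| 2% → 4% | 82.2% | 74.1% |
| 3% → 6% | 70.4% | 63.5% |

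SAP 8.7 allows Chi2 or Fisher as appropriate. Using Chi2 only when expected counts are at least 5, and Fisher otherwise, the miss rate at 1% → 2% is 91.7%. With 225 per arm after 10% loss it is 94.4% (Fisher) or 87.5% (Chi2). The formula in step 1 gives about 2319 per arm for 80% power to detect 1% v 2%.

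**3. What an interval would show.** The Newcombe interval for a risk difference d = p₁ − p₂ uses the Wilson limits (l, u) of each arm:

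lower = d − √[(p₁−l₁)² + (u₂−p₂)²]; upper = d + √[(u₁−p₁)² + (p₂−l₂)²].

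For 5/250 v 2/250: p₁ = 2.0% with Wilson limits 0.86% to 4.60%; p₂ = 0.8% with limits 0.22% to 2.87%; d = 1.2 points.
- Lower: 1.2 − √(1.14² + 2.07²) = 1.2 − 2.36 = −1.2.
- Upper: 1.2 + √(2.60² + 0.58²) = 1.2 + 2.66 = +3.9.

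| SAEs, prednisolone v placebo | Fisher p | Difference, points | 95% CI, points |
|---|---|---|---|
| 0 v 0 | 1.00 | 0 | −1.5 to +1.5 |
| 5 v 2 | 0.45 | +1.2 | −1.2 to +3.9 |
| 10 v 5 | 0.29 | +2.0 | −1.2 to +5.4 |

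None of these results is significant. They leave open true excesses of up to 1.5, 3.9 and 5.4 points respectively. The p-value does not show this; the interval does.

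**The case against.** The strongest reply is that SAP 8.7 already contains what a reader needs. Counts and percentages per arm are planned for AEs, serious AEs, related AEs and AEs leading to discontinuation, and anyone can compute a difference and interval from them. This stands as far as it goes. A reader might infer that safety is to be judged by a p-value alone, or that p>0.05 will be declared safe. The SAP says neither. The gap is that no estimate with an interval is pre-specified.

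A reader might also state flatly that the trial would miss a doubling of serious events nine times in ten. That holds only for a placebo SAE rate near 1%, which the documents do not supply. The figure is lower from about 2% upward and higher for rarer events.

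It is tempting to build an any-AE scenario by adding the 4.3–5.4% of minor side effects in Protocol 16.2 to a background rate. That figure is a frequency reported with short steroid courses, not an excess over placebo. The same section expects the risk to be reduced at the trial's dose, and no background rate is given.

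Three further points are fair. Low power for rare harms is a limit of size that no reporting change removes. Protocol 13.2 describes testing as possible for hypothesis-generating purposes. Protocol 15.3 and 12.6 add safety-board reviews and yearly safety reports, so 8.7 is not the only safety evaluation. None of these supplies a final between-arm estimate.

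SAP 8.6 does promise 95% intervals for proportions by the normal approximation. That text sits under secondary efficacy and concerns single proportions. The method also gives zero width at zero events, so it would not serve for rare SAEs.

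Finally, SAP 2 and 13 refer to output shells in Appendix 1, which were not among the documents. Intervals in those tables cannot be ruled out, but SAP 8.7 names none.

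**Conclusion.** The point holds as a gap in pre-specification. On a stated secondary objective, SAP 8.7 names a test and no estimate or interval, while the same SAP gives both for recovery. Across assumed placebo SAE rates of 0.5% to 3%, a true doubling would be non-significant in 64% to 99% of trials, depending on the rate and the test. A non-significant SAE comparison would therefore carry little information about harm.

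The miss rates rest on the assumed placebo rates, 250 evaluable children per arm and independent binomial counts. The gap in the text does not depend on them. The primary analysis, the sample size and the efficacy conclusions are unaffected. This is a cheap and worthwhile improvement, not a fault that undermines the trial.

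One might go further and let the upper confidence limit decide whether the drug is safe. The documents set no margin, so that would not be a usable rule. The interval should be reported as an estimate of what remains compatible with the data.

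**What to change.** In SAP 8.7, for patients with at least one related AE (the declared safety endpoint), any AE, any SAE and any AE leading to discontinuation, report the risk difference, prednisolone minus placebo, with a two-sided 95% confidence interval by a method suited to rare events (Newcombe or Miettinen-Nurminen). Keep the Chi2 or Fisher p-value as descriptive. Add one sentence saying that p>0.05 will not be reported as evidence of no harm. Make the same change in the Appendix 1 shells if they do not already show intervals.

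The cost is one or two sentences and one extra column in the AE table, with no new data, visits or patients. The safety statement becomes slightly less reassuring.
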